## Protocol Synopsis

Title	Randomized, Placebo-Controlled, Phase 3 Trial of RHB-102 (Ondansetron 24 mg Bimodal Release Tablets) for Presumed Acute Gastroenteritis or Gastritis
Study location	US multicenter
Study drug	RHB-102 (Ondansetron 24 mg Bimodal Release Tablets)
Comparator	Placebo
Rationale	
Ondansetron was the first 5-HT3 antagonist approved as an antiemetic. It has been approved for use for prevention and treatment of nausea and vomiting due to cytotoxic chemotherapy and radiotherapy, as well as for prevention of postoperative nausea and vomiting. Despite several clinical trials and much anecdotal evidence of efficacy against acute gastroenteritis, no formulation of ondansetron or any other 5-HT3 antagonist has ever been approved by the FDA for this indication.
 
RHB-102 is a modified release oral tablet formulation of ondansetron. It contains 6 mg ondansetron for immediate release and 18 mg in an extended release core. It provides early ondansetron levels similar to a single 8 mg immediate release tablet and sustained release over a 24-hour period. This should enable once daily dosing, so that a single dose of RHB-102 should be sufficient to control nausea and vomiting from acute gastroenteritis for most patients.
 
A variety of agents are used for symptomatic treatment of acute gastritis and gastroenteritis. The most commonly used non-5-HT3 antiemetics, prochlorperazine and promethazine, while reasonably effective may cause significant adverse events much more commonly than ondansetron. In recent published studies of patients with acute gastroenteritis, 50% or more who receive placebo do not vomit during the study observation period. Thus, patients may be exposed to potential toxicity without therapeutic benefit. Therefore, use of a placebo with rescue is justified in this situation.
 
Ondansetron causes side effects in few patients, but gastroenteritis patients administered intravenous or immediate release oral ondansetron frequently require multiple doses to control their symptoms. Thus, use of a modified release formulation may be of considerable benefit by providing rapid relief of symptoms and maintaining relief without need for redosing over the course of the illness, which is usually approximately one day.

Objectives	
Primary:	Comparison of the proportion of patients who are treatment successes, i.e., fulfill all three of the following criteria: a) without further vomiting, b) without rescue medication, and c) who were not given intravenous hydration $\geq 30$ minutes after the first dose of study medication through 24 hours after the first dose of study medication.
Secondary:	
Comparison between ondansetron and placebo groups of
 
 
• Treatment success, as defined above, through 4 days following first dose of study medication
 
• Proportion of patients who experience each of the components of treatment failure: 
 
○ Vomiting
 
○ Rescue antiemetic therapy
 
 
 

	
 
○ Intravenous hydration
 
• Severity of nausea
 
• Diarrhea as reported by 
 
○ Bristol Stool Scale (BSS, Appendix I): number and distribution by grade of grade <math>\geq 5</math> stools daily throughout the study
 
○ Stool consistency, as recorded per original protocol, none/formed (normal)/soft/watery (diarrhea)
 
 
 
• Incidence and severity of other symptoms of gastroenteritis
 
• Time from first dose of study medication to discharge from ED, extended observation unit or hospital, whichever comes last
 
• Time to resumption of normal activities (work/school/household)
 
• Proportion of patients requiring hospitalization
 
• Proportion of patients returning to emergency department for gastrointestinal symptoms within 4 days of initial discharge
 
• Adverse events
 

Population	
Adults and children <math>\geq</math> age 12 with vomiting from presumed acute gastroenteritis or gastritis of <math>\leq 36</math> hours duration
 
Inclusion criteria:
 
 
• Patients must have vomited at least twice in the 4 hours preceding signing informed consent
 
• A vomiting episode is defined as an episode of forceful expulsion of stomach contents. Retching if a patient has already emptied his or her gastric contents is also considered a vomiting episode. A distinct episode is characterized by a clear break in vomiting activity of at least 5 minutes
 
• Emesis must have been nonbloody (streaks of blood presumed due to force of retching are allowed)
 
• All patients (or a parent or guardian for patients <math><</math> age 18) must sign informed consent. Patients <math><</math> age 18 must also sign assent.
 
 
Exclusion criteria:
 
 
• Severe dehydration
 
 
For purposes of this study, severe dehydration is defined as two or more of the following criteria in the presence of decreased intake and increased output due to vomiting or diarrhea:
 
 
○ Absent or severely decreased urine output,
 
○ Weak pulse and/or low blood pressure,
 
○ Parched mucous membranes,
 
○ Lethargy, confusion, delirium or loss of consciousness.
 
 
 
• Signs and symptoms severe enough to require immediate parenteral hydration and/or parenteral antiemetic medication
 
• Temperature <math>> 39.0^{\circ}\text{C}</math>
 
• Likely etiologies for acute vomiting and diarrhea other than acute infectious or toxic gastroenteritis or gastritis 
 
○ This includes signs of an acute abdomen, which may require surgical intervention
 
 
 

	
 
Chemically-induced gastroenteritis, e.g., from alcohol, other drugs of abuse or other irritant chemicals
 
Use within 24 hours of study entry of specific medication for treatment of nausea and/or vomiting, e.g., 5-HT3 antagonists or phenothiazines, or receipt of any IV fluid for any reason. Nonspecific gastrointestinal remedies, such as antacids, proton pump inhibitors and homeopathic remedies, are permitted.
 
Congestive heart failure, bradyarrhythmia (baseline pulse<55/min), known long QT syndrome
 
Patient who have known QTc prolongation>450 msec, noted on prior or screening ECG, or who are taking medication known to cause QT prolongation 
 
Note: For current list of medications known to cause QT prolongation see: https://www.crediblemeds.org/healthcare-providers/drug-list/ Use list showing drugs with known risk of TdP.
 
 
 
Known underlying disease which could affect assessment of hydration or modify outcome of treatment, e.g., renal failure, diabetes mellitus, liver disease, alcoholism 
 
Patients with type 2 diabetes mellitus controlled by diet or oral medications and whose baseline blood glucose is <200 may be entered into the study
 
 
 
Abdominal surgery within the past 3 months
 
History of bariatric surgery or bowel obstruction at any time
 
Hypersensitivity or other known intolerance to ondansetron or other 5-HT3 antagonists
 
Patient has taken apomorphine within 24 hours of screening
 
Patient has previously participated in this study
 
Patient has participated in another interventional clinical trial, for any indication, in the past 30 days
 
For women of childbearing potential: documented or possible pregnancy. See body of protocol for detailed definition.
 

Design	Randomized, double-blind, placebo-controlled, parallel group study
Methodology	
Patients presenting to the emergency department who fulfill entry criteria will be asked to participate. Qualifying patients, once they have signed consent, will be stratified by age (<math>\geq</math> vs <age 18) and randomized 60:40 to RHB-102 or matching placebo.
 
Patients will receive one oral dose of study medication as soon as feasible. If a patient vomits within 15 minutes of the initial dose of study medication, he/she will receive a second dose. If a patient vomits again, regardless of how long after the second dose of study medication, no further study medication will be administered.
 
Patients vomiting <math>\geq</math>30 minutes after the first dose of study medication may receive rescue antiemetics, either parenterally or orally. In addition, a) patients with severe nausea <math>\geq</math>30 minutes after dosing with study medication and who in the treating physician's opinion require treatment, may receive rescue medication. b) These patients may receive intravenous hydration in addition to or in place of parenteral antiemetics if they are unable to tolerate oral hydration. However, only severely symptomatic patients clearly unable to tolerate oral hydration may receive intravenous hydration.

	
Any patient receiving rescue medication or parenteral hydration will be deemed a treatment failure.
 
Metoclopramide 0.3 mg/kg, maximum dose 10 mg, administered intravenously will be the default rescue medication. Oral metoclopramide or other antiemetics administered either intravenously or orally may be used at the investigator's discretion. However, patients are not to receive ondansetron or other 5-HT3 antagonists by any route for at least 24 hours after administration of study medication. The following 5-HT3 antagonists are available in the US: alosetron (Lotronex), dolasetron (Anzemet), granisetron (Sancuso and others), ondansetron (Zofran, Zuplenz and others), palonsetron (Aloxi).
 
Oral fluids will be administered as tolerated once a patient has not vomited for 30 minutes after dosing with study medication (second dose for those patients receiving 2 doses in the ED). Guidelines for administration of oral fluids are shown on page 20, section 4.4.1, of the protocol.
 
Patients tolerating oral fluids will be discharged once deemed stable by the attending physician but not prior to 4 hours after dosing. On discharge, patients will be given 3 additional doses of study medication to take once daily if necessary.
 
Patients who do not tolerate oral fluids may receive parenteral hydration. Data will be collected daily for up to 4 days following study initiation (until symptoms have resolved) to ascertain whether the patient had further vomiting, other sequelae of the acute gastroenteritis or required further medical care for the gastroenteritis. Data may be collected by entry by the patient or a caregiver into a web-based system or on paper, or by telephone contact daily from a study staff member. If during the follow-up period, symptoms progress or worsen or new symptoms develop, the patient may be asked to return for further evaluation. If by day 4 after discharge (i.e., the day after the last dose of study medication), the patient still notes gastroenteritis symptoms, he or she will be instructed to return for further evaluation.

Endpoints Efficacy:	
Primary:
 
Absence of vomiting without use of rescue medication or parenteral hydration from 30 minutes through 24 hours after the first dose of study medication.
 
Secondary:
 

• Treatment success, as defined above, through 4 days following first dose of study medication

• Individual components of treatment failure through 4 days following first dose of study medication:

◦ Vomiting

◦ Requirement for rescue antiemetic

◦ Treatment with intravenous hydration

• Severity of nausea

• Diarrhea will be reported in two ways:

◦ Bristol Stool Scale (BSS): number and distribution by grade of grade <math>\geq 5</math> stools daily throughout the study

◦ Stool consistency, as recorded per prior versions of protocol, none/formed (normal)/soft/watery (diarrhea)

• Incidence and severity of other symptoms of gastroenteritis, as recorded in CRF and patient diaries

• Time from first dose of study medication to discharge from ED, extended observation unit or hospital, whichever comes last

	
 
• Time to resumption of normal activities (work/school/household)
 
• Hospital admission
 
• Return to emergency department for gastrointestinal symptoms
 
• 
 

Safety:	Incidence and severity of adverse events through time of last follow-up call
Statistics	
Successful treatment is absence of further vomiting from 30 minutes through 24 hours after initial administration of study administration without use of rescue antiemetic or parenteral hydration. It is expected that 40% of the placebo group and 20% of the ondansetron group will fail therapy. To demonstrate a statistically significant difference with two-tailed p value=0.01 and power=90%, 320 patients will be entered into the study, 192 randomized to RHB-102 and 128 to placebo.
 
Patients will be stratified by age (< or <math>\geq</math> age 18) at baseline.
 
Patient demographics and disease characteristics will be summarized with descriptive statistics.
 
Safety and efficacy analyses will be based on all patients who receive any study medication.
 
A subgroup of patients, as defined in section 7.2 of the protocol, will also be evaluated for efficacy.
 
The incidence of treatment failure (vomiting, use of rescue medication or parenteral hydration from 30 minutes through 24 hours after initial administration of study medication) will be compared by Mantel-Haenszel test.
 
No interim analysis will be conducted.

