cPrior to discharge, patients will be given diary pages to record their course after discharge. Patients will be contacted each day following treatment to a maximum of 4 days to determine whether they had further nausea and vomiting after leaving the emergency department, the occurrence and quality of bowel movements, including assessment using the Bristol stool scale (Appendix I), and the nature, occurrence and severity of other symptoms, whether they required further care for the acute gastroenteritis, and details regarding the continuation, if any, of the illness. If symptoms persist for 3 or more days after study entry, the patient is to be instructed to return for further evaluation.

dTo include all medications taken within 7 days prior to study entry, all treatments (including parenteral fluids) on the day of study entry, and all medication, including rescue medications, from the time of study entry through last follow-up.

ePatients are to receive the first dose of study medication within one hour of signing informed consent.

fPatients may take study medication daily for up to 3 days after study entry (maximum total of 4 doses, plus one additional if patient vomits within 15 minutes of first dose) if symptoms persist. Patients should stop taking study medication if symptoms have resolved, though they may resume study medication once daily if symptoms recur after discontinuation. Patients are not to take any remaining study medication after day 4. They will be given mailers to return any unused study medication.

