#### 4.5 Duration of Treatment

On discharge, patients who have not had further vomiting and have not required rescue medication in the emergency department will be given 3 additional doses of study medication to take once daily if necessary. Patients will be instructed to take additional study medication if they are nauseated (whether persistent or recurrent) or have any vomiting. However, patients are not to take study medication more than 3 days after study entry. Thus, if a patient receives an initial dose of study medication in the emergency department, feels well the next day and does not take study medication, but subsequently has a recurrence of symptoms, that patient may not take the remaining dose of study medication on day 5. Rather, the patient should return for reassessment during the follow-up period.

Patients or their caregivers are to complete a diary each day for 4 days, recording episodes of vomiting, diarrhea, presence and severity of nausea, presence/development of other signs or symptoms related to the gastroenteritis, and occurrence of adverse events. This diary may be completed either on paper or through a web-based system. Alternatively, patients or their caregivers will be contacted daily for up to 4 days following study initiation (until symptoms have resolved) to ascertain whether the patient had further vomiting, other sequelae of the acute gastroenteritis or required further medical care for the gastroenteritis. If symptoms persist for 3 days after study entry, the patient will be instructed to return for further evaluation on the third or fourth day.

For patients discharged prior to 8:00 pm, the ED day diary page is to be completed. The ED day diary page is to include only information regarding events after discharge from the ED; information on events during the patient's ED stay is not to be repeated in the diary. For those discharged 8:00 pm to midnight, or later, diary information is to be recorded only on the follow-up diaries. But vomiting episodes and adverse events occurring between 8:00 pm and midnight the preceding day should be included in the information captured.

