#### 5.2.3 Procedures after discharge from emergency department:

Any patient who has a post-dosing ECG showing QTc>500 msec must have a follow-up ECG within 72 hours of initial dosing showing resolution of the QTc prolongation. This may be performed on an inpatient or outpatient basis at the investigator's discretion. If the QTc does not decrease below 500 msec during initial follow-up, the medical monitor must be contacted to discuss further follow-up.

If a patient vomits from 30 minutes after taking the first dose of study medication until 24 hours after the first dose of study medication or requires rescue antiemetic or parenteral hydration during that period, even without vomiting, he or she will be considered a treatment failure. In that case, the only post-emergency department follow-up will be a call 72-96 hours after discharge from the emergency department to ascertain whether the patient's symptoms have

resolved, whether any adverse events occurred, and whether the patient required further medical follow-up, either in an emergency department or other medical facility.

Prior to discharge, patients who are treatment successes (i.e., no vomiting, no rescue medication and no parenteral hydration while in emergency department) will be given a diary card to record:

- all episodes of vomiting and bowel movements, with description of each bowel movement
- severity of nausea (on a 5-point Likert scale) three times a day: before breakfast or the time at which the patient usually eats breakfast, between 1:00-2:00 pm, and at bedtime
- any symptoms the patient may have related to gastroenteritis, such as chills, fever, abdominal pain
- adverse events
- medications taken, either for gastroenteritis (study medication and others) or other conditions

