Patients will be contacted at least once daily for 4 days after discharge from the emergency department to question them about the presence of gastroenteritis symptoms and adverse events, to ask if and when they took study medication, and to ask whether they have returned to normal daily activities. The information recorded by the patient on his/her diary card will form the basis for data collected in the follow-up calls. If during the follow-up period, symptoms progress or worsen or new symptoms develop, the patient may be asked to return for further evaluation. If by day four after discharge (i.e., the day after the last dose of study medication), the patient still notes gastroenteritis symptoms, he or she will be instructed to return to see the investigator or his/her designate for further assessment. In addition, if the investigator is concerned that a patient may not be entering the data promptly and appropriately or as an added stimulus to data entry by the patient, the investigator may also contact the patient.

For patients returning due to persistent gastroenteritis 3 days after discharge from the ED, an interim history and physical examination will be performed. Laboratory studies may be performed if clinically indicated, and results of these studies will be entered into the CRF.

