7. ENDPOINTS AND COVARIATES

7.1. Efficacy Endpoint(s)

- 1) Primary Efficacy Endpoint: the proportion of patients who fulfill all the following 3 criteria from 30 minutes after first administration of study medication until 24 hours after the first dose of study medication:
 - a. absence of vomiting
 - b. no use of rescue medication, and
 - c. no intravenous hydration

If all of the above three criteria are fulfilled, the patient is considered a treatment success for the primary analysis. If one or more of the above three criteria are not fulfilled, i.e., the patient either experiences vomiting, receives rescue medication or receives intravenous hydration from 30 minutes through 24 hours after the first dose of study medication, the patient is considered a treatment failure.

Based on the 2nd blinded dry run conducted on [REDACTED], there were 28 subjects who did not have all the information needed to determine per the algorithm used if they met the primary endpoint successfully. For 17 patients, all treated under amendment 1 or 2, in which the primary endpoint was treatment success on emergency department discharge, the reason for not having complete information was the lack of an ER day diary. For these patients, based on all follow up data available, no treatment failure events occurred. Therefore, these patients are considered treatment successes. Among the other eleven, data were reviewed and several queries issued. Based on this review, patients were assessed by the medical monitor to be treatment successes (n=4), failures (n=1) or unknown (n=6). The adjudicated primary endpoint outcomes will be used for the primary analyses.

2) Secondary and Tertiary Efficacy Endpoints:

- Treatment success, as defined above, through 4 days following first dose of study medication
- Proportion of patients who experience or require each of the components of treatment failure:
 - Vomiting
 - Rescue antiemetic therapy
 - Intravenous hydration
- Severity of nausea
- Incidence and severity of diarrhea
- Incidence and severity of other symptoms of gastroenteritis
- Time from first dose of study medication to discharge from ED, extended observation unit or hospital, whichever comes last
- Days to resumption of normal activities (work/school/household)
- Proportion of patients requiring hospitalization
- Proportion of patients returning to emergency department for gastrointestinal symptoms within 4 days of initial discharge

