9.3. Efficacy Analyses for Secondary and Tertiary Endpoints

ITT population will be used for the analyses of all secondary and tertiary endpoints.

1) Analyses of Binary/Proportion Endpoint

Same statistical test as for the analyses of the primary endpoint, as stated in Section 9.2, will be used for analyzing other proportion endpoints.

2) Analyses of Time-to-Event Endpoints

Time to event endpoints will be compared between the treatment arms using stratified log-rank test adjusting the age stratification factor. The endpoints will also be summarized using the Kaplan-Meier method and displayed graphically when appropriate. Median event times and 2-sided 95% confidence interval for each median will be provided.

3) Analyses of Continuous Endpoints

Descriptive statistics, including the mean, standard deviation, median, minimum, and maximum values, will be provided for continuous endpoints.

4) Analyses of Ordinal Categorical Endpoints

The number and percentage of patients in each category will be provided for categorical endpoints. Bristol Stool Scale (BSS), added in the Protocol Amendment 3, is an 8 point ordinal categorical variable. Wilcoxon rank sum test will be used to compare the two treatment groups.

5) Concordance Assessment of Bristol Stool Scale and Stool consistency

Stool consistency, as recorded per original protocol, none/formed (normal)/soft/watery (diarrhea), is a 4 point ordinal categorical variable. Cross-tabulation of stool consistency and BSS among all the patients who have both assessments at a given time point will be created to evaluate the concordance of the two scales. Cohen's Weighted Kappa Coefficient and 95% confidence interval will be provided.

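### Return to normal activities is an ITT secondary endpoint, but the single follow-up call to 24-hour failures omits it and conflicts with the daily-contact text

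*Protocol*

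**What the plan says.** **The endpoint.** The Protocol Synopsis lists "Time to resumption of normal activities (work/school/household") among the secondary endpoints, and Protocol 2.2 and 7.4.4 list it too. SAP 7.1 words it as "Days to resumption of normal activities (work/school/household"). SAP 9.3 uses the ITT population for all secondary and tertiary endpoints, and its item 2 states: "Time to event endpoints will be compared between the treatment arms using stratified log-rank test adjusting the age stratification factor". It does not list which endpoints that rule covers.

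**Where it is asked.** The daily contacts in Protocol 5.2.3 are used "to ask whether they have returned to normal daily activities". This is the only instruction in either document to collect the item.

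**What failures get.** For a patient who fails between 30 minutes and 24 hours, Protocol 5.2.3 says that "the only post-emergency department follow-up will be a call 72-96 hours after discharge from the emergency department". The call covers symptom resolution, adverse events and further medical care.

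**The other collection lists.** None names activities:
- Synopsis, Methodology: data are collected "to ascertain whether the patient had further vomiting, other sequelae of the acute gastroenteritis or required further medical care for the gastroenteritis".
- Study Assessments, note c: nausea and vomiting, stools, "the nature, occurrence and severity of other symptoms, whether they required further care for the acute gastroenteritis", and continuation of the illness.
- Protocol 4.5: a diary "recording episodes of vomiting, diarrhea, presence and severity of nausea, presence/development of other signs or symptoms related to the gastroenteritis", plus adverse events. Contact by study staff is offered as an alternative to it.
- Protocol 5.2.3: the diary card, given to patients who are successes in the emergency department.

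**Who is contacted daily.** Note c, Protocol 4.1, the daily-contact paragraph of 5.2.3 and SAP 3.1 all say that patients are contacted daily, without excluding failures.

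**Missing data.** SAP 8 covers the primary endpoint and diary dates only.

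**The concern.** Whether a patient has a value for this endpoint can depend on whether that patient failed within 24 hours. Failure occurs after randomization and is the very thing the drug is meant to change. If failures have no value, the groups that remain are treatment successes on each arm: neither the ITT population nor a randomized comparison. Failures are also the patients one would expect to resume activities latest, so how they are handled can drive the result.

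Even for patients who are contacted daily, a yes/no answer dates the event only to the interval between two contacts. One missed contact widens that interval.

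**Working it through.** **1. Reproduce the plan's own figure.** No size is stated for this endpoint, so the check is on the source of the failure rates, Protocol 7.1: 40% v 20% failures, two-sided 0.01, 90% power, 60:40 allocation, 320 patients (192 + 128).

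With k = 1.5, the pooled rate is (0.40 + 1.5 × 0.20)/2.5 = 0.28.

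n(placebo) = [2.576 √(0.28 × 0.72 × (1 + 1/1.5)) + 1.282 √(0.24 + 0.16/1.5)]² / 0.20² = 126.3, rounded up to 127.

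RHB-102: 1.5 × 127 = 190.5, rounded up to 191. Total 318, which matches 320.

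**2. Patients without a scheduled question, if the single-call rule applies.**

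| | Placebo | RHB-102 | Total |
|---|---|---|---|
| ITT | 128 | 192 | 320 |
| 24-hour failures | 0.40 × 128 = 51.2 | 0.20 × 192 = 38.4 | 89.6 (28%) |
| Successes | 76.8 | 153.6 | 230.4 |

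**3. What each handling does.** Assumptions, none of them from the documents: exponential times to resumption with median 1 day in successes and 3 days in failures on both arms (so the drug acts only through failure), times rounded up to whole days, follow-up of 4 days, unstratified log-rank at two-sided 0.05.

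Share resumed by day 2 is 1 − 2^(−2/1) = 75% in successes and 1 − 2^(−2/3) = 37% in failures.

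| Handling of failures | Resumed by day 2, RHB-102 v placebo | Log-rank rejection |
|---|---|---|
| All have data | 0.8 × 75 + 0.2 × 37 = 67% v 0.6 × 75 + 0.4 × 37 = 60% | about 39% |
| Dropped, or censored before day 1 | 75% v 75% | about 5% |
| Kept as not resumed through day 4 | 0.8 × 75 = 60% v 0.6 × 75 = 45% | 92 to 93%, favouring RHB-102 |

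**4. Sensitivity to the assumptions.**
- Medians of 1.5 and 4 days: about 29% with full data, about 5% with failures dropped.
- Daily chance of resumption of 0.4 to 0.5 in successes and 0.15 to 0.25 in failures: 25 to 57% with full data, about 5% with failures dropped.
- Medians of 1 and 3 days plus an assumed direct hazard ratio of 1.4: about 98% with full data, about 63% with failures dropped.

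**The case against.** **Failures may be asked after all.** Note c, Protocol 4.1, the daily-contact paragraph of 5.2.3 and SAP 3.1 make no exception for failures. A reader might infer from the single-call sentence that failures are never asked; the documents do not settle that. What stands is a contradiction. The failure paragraph calls its one call the only follow-up, and the daily-contact paragraph, which sits just after the diary card for successes, does not say whom it covers. Patients who fail after discharge may also have had a daily contact first. If half of the failures had data (an assumption), rejection would be about 21%, against 38% with full data in the same run.

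**The diary gap is secondary.** It is tempting to conclude that a completed diary would leave the endpoint uncollected. Protocol 5.2.3 has the calls ask the question, with the diary feeding the calls. The gap matters only where the Synopsis and 4.5 let a diary stand in for calls. The case report form and diary are not in the documents and may carry the item, though the protocol text does not require it for failures.

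**Log-rank is not stated for this endpoint.** SAP 9.3 does not name it, and the wording in days could place it under continuous endpoints, which get descriptive statistics only. Log-rank is the more natural reading. Under either reading the same patients lack a value.

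**A vanishing effect is built in.** A reader might infer that dropping failures erases the drug's effect. That follows only from assuming no direct effect; with the hazard ratio of 1.4 above, power falls but does not vanish. Counting failures as not resumed inflates the result instead.

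**Conclusion.** The point holds as a conflict in the follow-up text together with a missing analysis rule. If the single-call paragraph is followed as written, about 28% of ITT patients lack this endpoint, 40% of placebo against 20% of RHB-102. Those shares rest on the plan's own failure rates and on no failure having been asked at an earlier contact. The comparison would then not be ITT, and its bias could go either way: from about 39% rejection to about 5% or to 92 to 93% under the assumed medians, depending on a choice that the SAP leaves open. The documents do not support a claim that failures are certainly not asked, nor that the effect disappears or is inflated in any particular amount.

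The stakes are moderate. This is one of about ten secondary and tertiary endpoints, with no power claim attached, and the primary endpoint is unaffected.

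**What to change.** **Protocol.**
- Reconcile the failure paragraph of 5.2.3 with note c, 4.1, the daily-contact paragraph of 5.2.3 and SAP 3.1, stating which contacts failures receive.
- Add one dated question to the 72 to 96 hour call: *Have you returned to normal activities? If yes, on what date?*
- Ask for the date in the daily contacts too, and carry the item on the diary wherever a diary may replace calls (Synopsis, 4.5).

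**SAP 9.3.**
- Name the endpoint as time-to-event and define the event date.
- Censor patients who have not resumed at their last contact.
- Do not drop failures, and do not count those without data as not resumed by default.
- Report the number of missing dates by arm and by 24-hour outcome.

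If the data are already collected, the analysis rules and the table of missing dates are still needed, with the result labelled as having rules set afterwards.

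**Cost.** One question in contacts already planned, and one diary line. The real drawback is uneven recall: failures give a date once, up to 4 days later, while successes are asked daily. Because failures are expected to be more common on placebo, the recall error falls unequally by arm and should be acknowledged when the result is reported.
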